10 ADVERSE EVENTS REPORTING AND DOCUMENTATION

10.1 Adverse Events

An adverse event (AE) is any untoward medical occurrence in a clinical investigation of a patient administered a pharmaceutical or supplement product and that does not necessarily have a causal relationship with the treatment. An AE is therefore any unfavorable and

unintended sign, symptom or disease temporally associated with the administration of an investigational product, whether or not related to that investigational product.

The study visits include a direct question for parents/caregivers regarding the occurrence of AEs since the last study visit. All information will be recorded in the site's source documents. Adverse events will be recorded in the patient CRF. Adverse events will be described by duration (start and stop dates and times), severity, outcome, treatment and relation to study supplement, or if unrelated, the cause.

AE Severity

The National Cancer Institute's Common Terminology Criteria for Adverse Events (CTCAE) Version 3.0 will be used to assess and grade AE severity.

Table 1. AE Severity Grading

Severity (Toxicity Grade)	Description
Mild (1)	Transient or mild discomfort; no limitation in activity; no medical intervention or therapy required. The subject may be aware of the sign or symptom but tolerates it reasonably well.
Moderate (2)	Mild to moderate limitation in activity, no or minimal medical intervention/therapy required.
Severe (3)	Marked limitation in activity, medical intervention/therapy required, hospitalizations possible.
Life-threatening (4)	The subject is at risk of death due to the adverse experience as it occurred. This does not refer to an experience that hypothetically might have caused death if it were more severe.

AE Relationship to Study Supplement

The relationship of an AE to the study supplement will be assessed using the guidelines in Table 2.

Table 2. AE Relationship to Study Supplement

Relationship to Supplement	Comment
Definitely	Previously known toxicity of agent; or an event that follows a reasonable temporal sequence from administration of the supplement; that follows a known or expected response pattern to the suspected supplement; that is confirmed by stopping or reducing the dosage of the supplement; and that is not explained by any other reasonable hypothesis.
Probably	An event that follows a reasonable temporal sequence from administration of the supplement; that follows a known or expected response pattern to the suspected supplement; that is confirmed by stopping or reducing the dosage of the supplement; and that is unlikely to be explained by the known characteristics of the subject's clinical state or by other interventions.

Possibly	An event that follows a reasonable temporal sequence from administration of the supplement; that follows a known or expected response pattern to that suspected supplement; but that could readily have been produced by a number of other factors.
Unrelated	An event that can be determined with certainty to have no relationship to the study supplement.

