2 STUDY RATIONALE

2.1 Risk / Benefit Assessment

Risk of treatment with folinic acid: In a prior randomized controlled trial of the same dose and duration of treatment with folinic acid in 48 children with ASD, there were no serious side effects and no side effects that were more common with folinic acid than placebo treatment.

Folinic acid is closely related molecule to the B vitamin, folate. It is approved to help with the adverse of effects of certain medications such as methotrexate, which depletes folate in the body. Folinic acid is also approved to be used in combination with chemotherapeutic agents in certain cancers. The identification of side effects of folinic acid is somewhat confounded by the combined use of potent chemotherapeutic drugs. Adverse effects of folinic acid may include: skin rashes, itching, facial flushing, nausea or vomiting. Acute allergic reactions have been reported – but considered rare.

Potential benefits: There is a possibility that children enrolled in this study will experience some beneficial effects related to treatment with folinic acid. As noted above, in a prior study of folinic acid in ASD, children were noted to have improvements in aberrant behavior and language development. Also, adult studies have found improvement in mood in patients treated with supplements containing folinic acid. Finally, there is biological plausibility that children with impaired cerebral folate transfer may have some beneficial physiological, and therefore clinical, effects when cerebral folate levels are raised through folinic acid treatment.

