7 STUDY TREATMENTS

Since this is an open-label study, all subjects will receive folic acid. Subjects, parents, teachers, and clinicians are not blinded to treatment status. There is no control product being used.

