13.2 Analysis of Secondary Endpoints

Secondary outcome measures will use the same spearman rank correlation test in Stata, comparing each urinary metabolite with each of the other outcome measures (SRS, PedsQL). Because this study is exploratory in nature, no adjustments will be made for multiple comparisons, as recommended by Rothman.⁵

Safety and tolerability data will be summarized in a tabular format, which will be included in the final study report/manuscript.

Adverse event rates will be coded by body system and MedDRA classification term. Adverse events will be tabulated by treatment group and will include the number of patients for whom the event occurred, the rate of occurrence, and the severity and relationship to study supplement.

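### On its natural reading, the Definitely row of Table 2 lets a known toxicity qualify without the row's other conditions, so common symptoms could be over-attributed to the supplement

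*Combined protocol and SAP*

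**What the plan says.** Section 10.1 states that the relationship of an adverse event to the supplement "will be assessed using the guidelines in Table 2". The table has four categories: *Definitely*, *Probably*, *Possibly* and *Unrelated*.

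The *Definitely* row begins "Previously known toxicity of agent; or an event that follows a reasonable temporal sequence from administration of the supplement". It then adds an expected response pattern and confirmation when the supplement is stopped or reduced, and it ends "and that is not explained by any other reasonable hypothesis". *Probably* asks for timing, pattern and the same confirmation, and for the child's clinical state or other interventions to be unlikely explanations. *Possibly* asks for timing and pattern, "but that could readily have been produced by a number of other factors". *Unrelated* is reserved for events where the absence of a link is certain.

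Section 2.1 says: "Adverse effects of folinic acid may include: skin rashes, itching, facial flushing, nausea or vomiting". Section 13.2 says the adverse event table will include "the rate of occurrence, and the severity and relationship to study supplement". Section 7 confirms: "There is no control product being used".

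**The concern.** A causality scale should become harder to satisfy as it rises. Here the highest category has an entry route that the lower ones lack. On the natural reading, an event that counts as a known toxicity meets *Definitely* even if the supplement was never stopped or reduced and another cause is at hand. The symptoms named in section 2.1 are also ordinary childhood complaints.

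The relationship column carries weight because the study has one arm. The synopsis, explaining why no interim analysis is planned, itself says that adverse event rates cannot be compared with placebo. Causal attribution within the study therefore rests largely on this rating. If the rating leans upward for common symptoms, so does the reported attribution. The categories also overlap, so two assessors who each follow the table could rate the same event differently.

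**Working it through.** The plan gives no figure to reproduce. The check is of the wording, followed by an illustration of size.

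**Step 1: the two readings.** Let K = known toxicity, T = plausible timing, P = expected pattern, D = confirmed on stopping or reducing, E = no other reasonable explanation.

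- Reading A: K or (T and P and D and E). The first limb stands alone.
- Reading B: (K or T) and P and D and E. The later conditions cover both limbs.

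*Probably* and *Possibly* both open with the timing phrase that follows the 'or' in *Definitely*, and both continue with a similar chain of conditions. That parallel ties the chain in *Definitely* to the second limb, which makes A the natural reading. Reading B is possible, but even there K substitutes for T, so the row still waives timing for a known toxicity.

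**Step 2: test events.** Each event is taken to be of a kind named in section 2.1, so K and P hold. *Possibly* is taken as T and P and not E. The last column is the amended row, T and P and D and E.

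| Timing plausible | Confirmed on stopping or reducing | No other explanation | *Definitely*, A | *Definitely*, B | *Possibly* | *Definitely*, amended |
|---|---|---|---|---|---|---|
| no | no | no | yes | no | no | no |
| yes | no | no | yes | no | yes | no |
| yes | yes | no | yes | no | yes | no |
| yes | yes | yes | yes | yes | no | yes |

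Under A, the second and third events fall in *Definitely* and *Possibly* together, and Table 2 has no tie-break. Under B or the amended row, that overlap disappears.

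**Step 3: illustration of size.** The number of children N is 20 expected and up to 40 allowed (synopsis, rationale for number of subjects). The share p with at least one such event from an unrelated cause is not in the documents. It is assumed here at 10–20%, with 5% as a lower check. Expected children = N × p. Chance of at least one = 1 − (1 − p)^N.

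| N | p | N × p | Chance of at least one |
|---|---|---|---|
| 20 | 5% | 1 | 1 − 0.95^20 = 0.642 |
| 20 | 10% | 2 | 1 − 0.90^20 = 0.878 |
| 20 | 20% | 4 | 1 − 0.80^20 = 0.988 |
| 40 | 5% | 2 | 1 − 0.95^40 = 0.871 |
| 40 | 10% | 4 | 1 − 0.90^40 = 0.985 |
| 40 | 20% | 8 | 1 − 0.80^40, above 0.999 |

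These are upper bounds for each assumed p, because they suppose that every such event is recorded and rated *Definitely* under A. The last column also assumes that children are independent. That is doubtful in one school where all children start on the same date (section 9.2). The expected counts do not need independence.

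**The case against.** The strongest reply is that this is loose drafting which a sensible assessor would correct. Table 2 is offered as guidelines, and a study investigator reviews the adverse event forms (section 8.1.4). Section 10.1 asks for the cause to be recorded when an event is unrelated, so non-drug causes are anticipated. A toxicity of the agent is arguably causal language already: vomiting from an infection resembles a toxicity without being one. Section 2.1 says only that the listed effects may occur. It also reports that the prior randomised trial found none more common than on placebo. Nowhere are these symptoms designated as known toxicities for Table 2. Counts, rates and severity do not depend on the row, the metabolite correlations are untouched, and over-attribution is the cautious direction of error.

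Much of this stands, and it limits the claim. It does not remove the defect, because the reviewer is pointed to this table and its top row is at best ambiguous.

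A reader might also infer that timing is wholly irrelevant, so that a stomach upset in the month after stopping must be rated *Definitely*. The documents do not support that. The adverse event definition covers events "temporally associated with the administration of an investigational product, whether or not related to that investigational product". This is a weak limit, since it governs what is recorded rather than how it is attributed, but it is a timing element. Collection in that month is also unclear: Appendix 1 marks adverse experiences at Visit 5, while section 9.5 lists no adverse event form and sections 4.3 and 8.1.4 specify questioning at 1 and 3 months.

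**Conclusion.** The point holds as a wording defect with a possible upward bias. On its natural reading, the *Definitely* row admits a known toxicity without the conditions after the 'or'. It is then looser than *Probably* and overlaps *Possibly* with no rule for choosing. Because relationship is reported without a comparator, symptoms such as vomiting or rash could be over-attributed to the supplement.

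The size cannot be derived from the documents. The figures of at most 2–4 of 20 or 4–8 of 40 children rest on an assumed 10–20% background incidence, on reading A, and on literal application by the assessor.

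A reader might go further and infer that the safety table will be filled with ordinary complaints presented as proven drug reactions. The documents do not support this: they give no background rate, the table is guidance applied by an investigator, and no text calls such events proven. The row should be corrected, but the defect does not affect the primary or secondary correlation analyses.

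**What to change.** Delete the stand-alone first limb of the *Definitely* row. The category should then require all of the following: plausible timing, a pattern known or expected for the supplement, confirmation on stopping or reducing, and no other reasonable explanation. A known toxicity, including the effects named in section 2.1, would count only as evidence for the pattern condition.

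This is a one-line change to Table 2, carried through to the adverse event form. It needs no extra data. The cost is that fewer events will reach *Definitely*, and some will move to *Probably* or *Possibly*.

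One consequence should be settled in the same edit. A listed symptom with plausible timing and no other explanation, but without confirmation on stopping or reducing, would strictly meet none of the four rows. Symptoms outside the list already face that gap, so the table should say where such events go.

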10.2 Serious Adverse Events (SAE)

An SAE is defined as any AE occurring at any dose that results in any of the following outcomes:

- death
- a life-threatening adverse experience
- inpatient hospitalization or prolongation of existing hospitalization
- a persistent or significant disability/incapacity
- a congenital anomaly/birth defect

Other important medical events may also be considered an SAE when, based on appropriate medical judgment, they jeopardize the subject or require intervention to prevent one of the outcomes listed.

10.3 Serious Adverse Experience Reporting

We will document all SAEs that occur (whether or not related to study supplement) per [UCSF CHR Guidelines](#). The collection period for all SAEs will begin after informed consent is obtained and end after procedures for the final study visit have been completed.

We will report all AE's and SAE's according to UCSF CHR guidelines.

11 EARLY DISCONTINUATION OF STUDY SUPPLEMENT

A subject may be discontinued from study treatment at any time if the subject, the investigator, or the Sponsor feels that it is not in the subject's best interest to continue. The following is a list of possible reasons for study treatment discontinuation:

- Participant legal guardian withdrawal of consent.
- Participant is not compliant with study procedures.
- Adverse event that in the opinion of the investigator would be in the best interest of the participant to discontinue study supplement.
- Protocol violation requiring discontinuation of study treatment.
- Lost to follow-up.

If a participant is withdrawn from treatment due to an adverse event, the subject will be followed and treated by the Investigator until the abnormal parameter or symptom has resolved or stabilized.

All participants who discontinue study supplement will be asked to continue the outcome assessment as scheduled.

11.1 Withdrawal of Subjects from the Study

All subjects are free to withdraw from participation at any time, for any reason, specified or unspecified, and without prejudice.

Reasonable attempts will be made by the investigator to provide a reason for subject withdrawals, and this information will be recorded in the subject's source documents.

12 PROTOCOL VIOLATIONS

A protocol violation occurs when the subject, or investigator, fails to adhere to significant protocol requirements affecting the inclusion, exclusion, subject safety and primary endpoint criteria. Protocol violations for this study include, but are not limited to, the following:

- Failure to meet inclusion/exclusion criteria.
- Improper use of schedule/dose of study supplement.

When a protocol violation occurs, it will be discussed with the investigator and a Protocol Violation Form detailing the violation will be generated. This form will be signed by the Investigator and reported to the UCSF CHR according to established guidelines.

13 STATISTICAL METHODS AND CONSIDERATIONS

Prior to the analysis of the final study data, a detailed Statistical Analysis Plan (SAP) will be written describing all analyses that will be performed. This information will be posted on clinicaltrials.gov to ensure that data analysis proceeds as defined a priori. Any modifications to the plan provided below will be noted on clinicaltrials.gov before the first subject is enrolled.

13.1 Analysis of Primary Endpoint

The primary analysis in the study is the correlation between the mean change in each urinary metabolite and the mean change in participant behavior as measured by the ABC using the spearman rank correlation test in Stata. The primary outcome measure is the correlation between urinary metabolites and the total ABC score.

13.2 Analysis of Secondary Endpoints

Secondary outcome measures will use the same spearman rank correlation test in Stata, comparing each urinary metabolite with each of the other outcome measures (SRS, PedsQL). Because this study is exploratory in nature, no adjustments will be made for multiple comparisons, as recommended by Rothman.⁵

Safety and tolerability data will be summarized in a tabular format, which will be included in the final study report/manuscript.

Adverse event rates will be coded by body system and MedDRA classification term. Adverse events will be tabulated by treatment group and will include the number of patients for whom the event occurred, the rate of occurrence, and the severity and relationship to study supplement.

13.3 Sample Size

The study is designed to detect a correlation coefficient (Pearson's r) between the mean urinary metabolite change and the mean behavioral measure change of 0.6, which is considered to indicate a moderate-to-strong correlation. Using a two-sided alpha of 0.05 and a Beta of 0.1 (90% power), our required sample size is 25 participants to detect this degree of correlation. Since we may incur up to 20% dropout (5 participants), our target sample size is 30 participants, but we will allow up to 40 to provide the study opportunity to all children enrolled in the target school (Oak Hill School).

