PLANNED INTERIM ANALYSES	No interim analyses planned given the short-term duration of the study, the established safety of the treatment, and the lack of randomization (so no ability to compare rates of AE's between active and placebo treatment).
STATISTICS Primary Analysis Plan	Correlations between changes in mean levels of urinary metabolites and changes in mean behavioral measures (0 to 3 months) will be done using a spearman rank correlations test using STATA. We prospectively define correlations with an absolute value of ≥ 0.6 to be potentially involved in the mechanism of action. All metabolites with this correlation will be mapped to known metabolite pathways to examine pathway changes.
Rationale for Number of Subjects	We are recruiting all children currently enrolled at Oak Hill School (current enrollment = 36). We anticipate that we will enroll 20 students in the current study, but we will allow up to 40 (if school enrollment increases).

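### The 90% power in Section 13.3 is for a Pearson test at 25 participants; the planned Spearman test has about 87% there, and about 77% at the 20 students the synopsis expects

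*Combined protocol and SAP*

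**What the plan says.** Section 13.3 (Sample Size) sets the effect size on the Pearson scale: "The study is designed to detect a correlation coefficient (Pearson's r") of 0.6 between the metabolite change and the behavioural change. It continues: "Using a two-sided alpha of 0.05 and a Beta of 0.1 (90% power), our required sample size is 25 participants to detect" a correlation of that size. It then allows for up to 20% dropout and concludes that "our target sample size is 30 participants", with up to 40 permitted.

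The planned test is a rank correlation. Section 13.1 relates the change in each metabolite to the change in behaviour "as measured by the ABC using the spearman rank correlation test in Stata". The synopsis (Primary Analysis Plan) says the same: "changes in mean behavioral measures (0 to 3 months) will be done using a spearman rank correlations test using STATA". Section 13.2 uses the same test for the secondary outcomes, with no adjustment for multiple comparisons.

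Under Rationale for Number of Subjects, the synopsis expects 20 students to enrol out of a current school roll of 36, and allows up to 40.

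The synopsis also has a descriptive selection rule: "We prospectively define correlations with an absolute value of ≥ 0.6 to be potentially involved in the mechanism of action". The metabolites that meet it are mapped to pathways.

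**The concern.** The 90% is the only power figure in the documents. It belongs to a test that the plan does not use, and to a number of participants above the synopsis's own forecast. A reader who takes it as the chance of detecting a true correlation of 0.6 will overestimate that chance, slightly at 25 analysed and clearly at 20 or fewer. This bears on how a non-significant correlation is read: with 16 analysed, a true 0.6 would be missed about one time in three. The sample size section and the synopsis also give different pictures of how large the study will be, so the stated power is not tied to the number expected in the analysis.

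**Working it through.** **Inputs from the documents.** r = 0.6 (Pearson), two-sided alpha 0.05, power 90%, required 25, dropout 20%, target 30, maximum 40 (Section 13.3); Spearman test (Sections 13.1 and 13.2, synopsis); 20 expected (synopsis). With no multiplicity adjustment, 0.05 applies to each metabolite-score pair.

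**Assumption.** The documents give no joint distribution for the changes. The main figures take it as bivariate normal without ties.

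**Step 1: reproduce the 25.** By Fisher z for a Pearson correlation,

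n = ((1.960 + 1.2816) / atanh(0.6))² + 3 = (3.2416 / 0.6931)² + 3 = 21.87 + 3 = 24.87, so 25.

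The power at n = 25 is Φ(0.6931 × √22 − 1.960) = Φ(1.291) = 90.2%. The arithmetic in Section 13.3 is right for the test it names.

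**Step 2: numbers analysed.** 30 × 0.8 = 24 and 20 × 0.8 = 16.

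**Step 3: power of the planned test.** Under bivariate normality a Pearson r of 0.6 corresponds to a Spearman value of (6/π) × asin(0.3) = 0.582. A Spearman value of 0.6 corresponds to a Pearson r of 2 sin(0.1π) = 0.618. Power was simulated with 200,000 samples per setting, using the t approximation for the test. Simulation error is about 0.1 point.

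| Analysed | Pearson, Fisher z | Pearson, simulated | Spearman, true Pearson 0.6 | Spearman, true Spearman 0.6 |
|---|---|---|---|---|
| 16 | 70.5% | 73.5% | 65.3% | 68.5% |
| 20 | 81.5% | 83.6% | 76.8% | 80.1% |
| 24 | 88.8% | 90.1% | 85.0% | 87.8% |
| 25 | 90.2% | 91.3% | 86.7% | 89.1% |
| 30 | 95.0% | 95.5% | 92.5% | 94.3% |
| 40 | 98.8% | 98.9% | 97.8% | 98.5% |

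Spearman power at a true Pearson r of 0.6 is 89.4% at 27 and 90.5% at 28, so about 28 analysed are needed for 90%. As a cross-check, Fisher z with variance 1.06/(n − 3) gives 85.8% at 25 and 75.9% at 20.

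**Step 4: split the gap at 20.** From the stated 90% to 86.7% is 3.3 points for the change of test at n = 25. From 86.7% to 76.8% is 9.9 points for having 20 rather than 25. In the other order, by Fisher z, Pearson falls 90.2 − 81.5 = 8.7 points from 25 to 20, and the change of test at 20 then takes 81.5 − 76.8 = 4.7. In both orders the smaller number accounts for most of the gap.

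**Step 5: sensitivity to the distribution.** Two illustrative departures from normality were simulated.
- Bivariate t with 3 degrees of freedom and correlation parameter 0.6: Spearman power is about 81-82% at 25 and 72% at 20.
- Heavy tails in the metabolite only (sinh of a standard normal), raw-scale Pearson r of 0.6: sinh(Z) and Z correlate at e^0.5 / √((e² − 1)/2) = 1.649 / 1.787 = 0.922, so the underlying normal correlation is 0.6 / 0.922 = 0.650. Spearman power is then about 93% at 25 and 85% at 20, and heavier tails push it higher.

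Heavy tails can therefore move the figures either way.

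**The case against.** The case for leaving the text alone has several parts.

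- **The mismatch is small.** At 25 analysed it is about 3 points, or about 1 if 0.6 is read as a Spearman value. If all 30 targeted students are analysed, Spearman power is above the stated 90%. This stands, and it limits the weight of the point.
- **The shortfall at 20 is mainly about enrolment.** This also stands. Pearson power at 20 is already only about 82-84%. A reader might infer that choosing Spearman costs 13 points; Step 4 shows that it does not.
- **The figures depend on normality.** They do, and Step 5 shows that even the direction of the difference can change. That is a reason to state the assumption beside the figure. It does not justify leaving a Pearson figure to stand for a Spearman test.
- **The study is exploratory and recruits from one school.** Section 13.2 uses the exploratory label only to forgo multiplicity adjustment. Section 13.3 still states a formal power, which should describe the planned analysis.

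A reader might also infer that the plan claims 90% sensitivity for the 0.6 mapping rule and fails to deliver it. A true correlation of 0.6 does meet that rule only about 43-45% of the time (0.6 as Pearson) or 49% (0.6 as Spearman) for 16 to 40 analysed, because the cut-off sits at the true value. But no section attaches the 90% to that rule or draws any conclusion from a metabolite's absence from the map. The missing figure is useful detail, not an error.

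**Conclusion.** The point holds and is minor. The sample size calculation contains no arithmetic error. The stated power is simply not that of the planned test at 25, nor of either test at the enrolment the synopsis expects. Taking 0.6 as Pearson's r, as Section 13.3 does, Spearman power is about 87% at 25 analysed, 85% at 24, 92% at 30, 77% at 20 and 65% at 16. If 0.6 is a Spearman value, it is about 89% at 25 and 80% at 20.

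All of these figures are per metabolite-score pair at an unadjusted 0.05, and they assume bivariate normality with few ties. The inconsistencies themselves, Pearson against Spearman and 20 against 30, rest on the text alone. The sizes are conditional on that assumption.

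**What to change.** In Section 13.3, keep the Pearson calculation if wished, but label it as such and add the power of the planned Spearman test with its assumption. For example: under bivariate normality with few ties, power for one metabolite-score pair at a true Pearson r of 0.6 is about 87% with 25 analysed, 85% with 24, 92% with 30, 77% with 20 and 65% with 16; about 28 analysed are needed for 90%.

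Reconcile the synopsis's expected 20 with the Section 13.3 target of 30, so that the stated power matches the number expected in the analysis. The synopsis itself states no power figure, so only its enrolment text is affected. The SAP promised in Section 13 should carry the same statement.

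Optionally, add one sentence saying that the 90% does not apply to the 0.6 mapping rule, which a true correlation of 0.6 meets a little under half the time whatever the number analysed. Which rater's ABC total is primary is a separate question and should be raised separately.

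The change is wording only. It alters no test and no data collection. The downside is a slightly less favourable stated power.

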PRIMARY OBJECTIVE	To examine changes in urinary metabolites in children with ASD being treated with folinic acid and to determine if changes in urinary metabolites are correlated with clinical improvements.
SECONDARY OBJECTIVES	Develop a prediction model to determine which children are most likely to benefit from folinic acid.

NUMBER OF SUBJECTS	40
SUBJECT SELECTION CRITERIA	
Inclusion Criteria: Age 5-22, enrolled at Oak Hill School, diagnosis of autism established by DSM-IV criteria and clinician examination.
 
Exclusion Criteria: Seizure disorder, serious medical illness within the last 6 months as judged by the study PI. Known allergy to folate.

TEST PRODUCT, DOSE, AND ROUTE OF ADMINISTRATION	Folinic acid 2mg/kg per day (maximum 50mg/day) in two equally divided doses with half the target dose given during the first 2 weeks.
CONTROL PRODUCT, DOSE AND ROUTE OF ADMINISTRATION	There is no control product in this study.
DURATION OF SUBJECT PARTICIPATION AND DURATION OF STUDY	
Subjects will be on study for 4.5 months
 
Screening: up to 2 weeks.
 
Treatment: 3 months
 
Follow-up: 1 month (1 additional month after treatment)
 
The total duration of the study is expected to be 12 months. 3-6 months for subject recruitment; 4 months for final subject follow-up; 2 months for data analysis and manuscript preparation.

CONCOMITANT MEDICATIONS	
Allowed: all
 
Prohibited: none

EFFICACY EVALUATIONS	
Parent (Aberrant Behavior Checklist, Social Responsiveness Scale, Pediatric Quality of Life)
 
Teacher (Student Progress Form, Aberrant Behavior Checklist, Social Responsiveness Scale)
 
Urinary Metabolomics (Baseline and 3 months)

PRIMARY ENDPOINT	
 Correlation between mean change in Aberrant Behavior Checklist and mean change in urinary metabolites.
SECONDARY ENDPOINTS	
 Correlations between changes in urinary metabolites and all secondary outcome measures.
OTHER EVALUATIONS	None

SAFETY EVALUATIONS	All study subjects are enrolled at the Oak Hill School and will be observed all school days by teachers, who are aware of student participation in the study. Parents, teachers, and enrolled students will be advised to report any new medical problems to study investigators, who will evaluate all potential adverse events and report to the CHR according to established guidelines.

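### The 90% power in section 13.3 rests on 25 evaluable participants and a target of 30, but the synopsis expects 20, where Spearman power for a correlation of 0.6 is about 77-80%

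*Combined protocol and SAP*

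**What the plan says.** Section 13.3 (Sample Size) designs the study to detect a Pearson correlation of 0.6 between metabolite change and behavioural change: "Using a two-sided alpha of 0.05 and a Beta of 0.1 (90% power), our required sample size is 25 participants". It then allows for dropout: "Since we may incur up to 20% dropout (5 participants), our target sample size is 30 participants", with up to 40 allowed so that every child at the school can take part.

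The synopsis differs. Under Rationale for Number of Subjects it says: "We anticipate that we will enroll 20 students in the current study, but we will allow up to 40 (if school enrollment increases". The same entry gives the school's current enrolment as 36. The synopsis row "NUMBER OF SUBJECTS" lists 40. Section 5.1 gives 40 children in the ongoing outcomes study at the school.

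Three other statements bear on the point:

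- Section 13.1 tests the change in behaviour "as measured by the ABC using the spearman rank correlation test in Stata", so the planned test is Spearman's and not Pearson's.
- The synopsis Primary Analysis Plan selects metabolites by the size of the coefficient: "We prospectively define correlations with an absolute value of ≥ 0.6 to be potentially involved in the mechanism of action".
- Section 11 says: "All participants who discontinue study supplement will be asked to continue the outcome assessment as scheduled".

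**The concern.** The enrolment expected in the synopsis is below the number that section 13.3 says is required, even before any dropout. The 90% is therefore claimed for a study larger than the one expected.

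The figure tells a reader that a true correlation of 0.6 would be missed one time in ten for a given metabolite at p < 0.05. Anyone reading a null result for a folate-pathway metabolite would lean on it. If the miss rate is really two or three in ten, that null result says less than it appears to.

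The 90% could also be mistaken for the chance that a relevant metabolite reaches the pathway-mapping step. That step depends on |rho| ≥ 0.6 and not on p < 0.05, so the stated power does not describe it.

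**Working it through.** **Inputs.** Correlation 0.6, two-sided alpha 0.05, power 90%, required 25, dropout up to 20%, target 30, maximum 40 (section 13.3). Expected enrolment 20, school enrolment 36 (synopsis). Spearman test (synopsis and section 13.1). Section 13.2 makes no multiplicity adjustment, so alpha is taken as 0.05 per metabolite.

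**1. The plan's own figure.** Fisher z for Pearson's r:

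n = ((1.9600 + 1.2816) / atanh(0.6))² + 3 = (3.2416 / 0.6931)² + 3 = 24.87, rounded up to 25.

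The 25 reproduces. Power at 25 is Φ(√22 × 0.6931 − 1.960) = 90.2%.

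**2. The same method at the expected enrolment.**

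- n = 20: Φ(√17 × 0.6931 − 1.960) = 81.5%.
- n = 16 (20 × 0.8): Φ(√13 × 0.6931 − 1.960) = 70.5%.

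**3. The planned test.** Spearman power was simulated with bivariate normal data, the two-sided t-approximation p-value and 200,000 datasets per cell. The 0.6 can be read in two ways. As Pearson r = 0.6, the population Spearman rho is (6/π) × arcsin(0.3) = 0.582. As Spearman rho = 0.6, the Pearson r is 2 × sin(0.6π/6) = 0.618.

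| Evaluable n | How it arises | Pearson, Fisher z | Spearman, r = 0.6 | Spearman, rho = 0.6 |
|---|---|---|---|---|
| 16 | 20 less 20% | 70.5% | 65.1% | 68.8% |
| 20 | 20, no dropout | 81.5% | 76.8% | 79.9% |
| 24 | 30 less 20% | 88.8% | 85.0% | 87.7% |
| 25 | required in 13.3 | 90.2% | 86.8% | 89.1% |
| 26 | | 91.4% | 88.1% | 90.4% |
| 28 | 36 less 20% (28.8, rounded down) | 93.4% | 90.5% | 92.4% |
| 32 | 40 less 20% | 96.2% | 94.2% | 95.5% |

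At n = 27 with r = 0.6, power is 89.4%. So 90% needs 26 evaluable (rho = 0.6) or 28 (r = 0.6).

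As a cross-check, Fisher z for a Spearman rho of 0.6 with variance 1.06/(n − 3) gives 79.3% at 20 and 68.0% at 16. The more conservative variance (1 + 0.6²/2)/(n − 3) gives 74.9% and 63.3%. Neither changes the conclusion.

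**4. Dropout allowance.** Section 13.3 adds 20% of 25 to 25. But 20% lost from 30 leaves 24, and 25/0.8 = 31.25, rounded up to 32. For the Spearman requirement, 26/0.8 = 32.5, rounded up to 33, and 28/0.8 = 35.

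**5. Participation implied.** A target of 30 is 30/36 = 83% of the students (30/40 = 75% on the section 5.1 figure). The expected 20 is 20/36 = 56% (20/40 = 50%).

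**6. The selection rule.** The critical |rho| for p < 0.05 is t/√(n − 2 + t²), where t is the 97.5% point on n − 2 degrees of freedom. It is 0.497 at n = 16, 0.444 at 20 and 0.396 at 25. All are below 0.6, so the selection rule is stricter than the test. The chance that the observed |rho| reaches 0.6 when the true correlation is 0.6 is 45.2%, 44.7%, 44.0% and 43.3% at n = 16, 20, 24 and 32 (r = 0.6), or 49.1%, 48.8%, 48.7% and 48.8% (rho = 0.6).

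**The case against.** The best defence is that 20 is an expectation and not a cap. Up to 40 may enrol, and at 32 evaluable power exceeds 90% on any reading. Dropout is stated as a ceiling, and those who stop the supplement are asked to stay in follow-up, so 16 is pessimistic. The study is called exploratory and recruits everyone it can, so a power figure changes nothing that is done. It can also be said that Spearman figures overstate the conflict, since the protocol's own method gives 81.5% at 20.

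Part of this stands:

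- The 16 is a worst case for an enrolment of 20 and not a forecast. It is not fully ruled out by section 11, which speaks of outcome assessments and does not name the month-3 urine that the primary endpoint also needs.
- The 40 is explained as a maximum in both places. The real conflict is between 20 and 30, and the documents do not show which is current.
- The dropout slip (24 against 25) and the Pearson-Spearman difference (one to three participants) are small.
- The participation percentages use all enrolled students and not only those eligible.
- The |rho| ≥ 0.6 result hardly varies with n, so it is no argument for one enrolment over another. It matters only because it limits what the power statement means.

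None of this removes the conflict. The 90% is not reached at 20 by Pearson or by Spearman, and the synopsis ties the upper limit to growth in school enrolment. An exploratory aim explains the lack of multiplicity adjustment, but it does not make a stated power correct.

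**Conclusion.** The concern holds. It is an inconsistency between the synopsis and section 13.3. The calculation of 25 is itself right for Pearson's r.

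At the expected 20, Spearman power is about 77-80% with no dropout and about 65-69% in the worst case. The miss rate is thus 20-23%, or 31-35%, against the stated 10%. At the section 13.3 target of 30 less 20%, power is 85-88%, just under the claim. It passes 90% if enrolment nears 40.

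These figures are for a single metabolite at unadjusted two-sided 0.05 and assume bivariate normality, which the protocol does not state. Each range covers the two readings of 0.6.

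The power statement should be corrected. The design is not invalidated.

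**What to change.** The sponsor should say which expected enrolment applies, use it in both the synopsis and section 13.3, label 40 as the maximum in the synopsis row, and restate power for the Spearman test. Suggested text, to be adapted if 30 proves to be the current figure:

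> Expected enrolment is 20 students, with a maximum of 40. For a single metabolite (Spearman test, two-sided alpha 0.05, true correlation 0.6, bivariate normality assumed), power is about 77-80% with 20 evaluable and about 65-69% with 16 (20 enrolled, maximum 20% dropout). It is about 85-88% with 24 (30 enrolled less 20%) and about 94-96% with 32 (40 enrolled less 20%). About 26-28 evaluable are needed for 90%, or 33-35 enrolled at 20% dropout, using n/(1 − d). This power refers to p < 0.05 and not to the |rho| ≥ 0.6 selection rule, which a true correlation of 0.6 meets about 43-49% of the time.

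The cost is wording in the synopsis and section 13.3. Enrolment and analysis do not change. The stated power becomes less favourable at the expected enrolment.
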